STEP 3 – **Identification of patients exposed to anifrolumab for the outcome-specific source** population

At step 3, the malignancy and serious infection source populations will be created.

Step 3a. Exposed patients in the malignancy source population

Additional exclusion criteria to be applied to the exposed patients:

• A diagnosis of any malignancy prior to index date.

³ According to the SLE severity algorithm, most moderate to severe patients will be those with a previous exposure to SOC indicated for moderate to severe disease. A very small group of patients, defined as having moderate/severe SLE based on the existence of SLE-related comorbidities, will not have a prescription of SOC for moderate/severe SLE.

Step 3b. Exposed patients in the serious infection source population

Additional exclusion criteria to be applied to the exposed patients:

- A diagnosis of any malignancy prior to index date.
- A diagnosis of HIV/AIDS or congenital immunodeficiency prior to index date.
- Organ or bone marrow transplant procedure prior to index date.
- A diagnosis of serious infection in the previous 6 months.

STEP 4 – **Time-based exposure sets**

This step is defined to create the time-based exposure sets, from the outcome-specific source populations. For each patient exposed to anifrolumab (identified in steps 3a and 3b) all unexposed patients from the source population (step 2b) that meet the following criteria will be included as unexposed patients.

Step 4a. Malignancy time-based exposure set

Patients exposed to anifrolumab from the malignancy source population (step 3a) and patients unexposed to anifrolumab (step 2b). Inclusion criteria for patients unexposed to anifrolumab (exposed to SLE SOC):

- At least a prescription of SOC indicated for moderate to severe SLE (Table 14).
- Duration of the previous exposure to SLE SOC similar to the SLE SOC duration of the corresponding exposed patient (+/- 45 days [wider time intervals may be considered if matches cannot be obtained using this time window]), at index date. The **index date** for the patient unexposed to anifrolumab will be the SLE SOC prescription date that will result in length of the SLE SOC treatment closer to SLE SOC treatment of the corresponding exposed patient.
- No prescription for anifrolumab prior to index date.
- A minimum data availability of 12 months prior to index date.
- Age ≥ 18 years at index date.

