10.3.2.2 Serious infections

Serious infections are generally defined as those that result in death, are life-threatening; require inpatient hospitalisation or prolongation of existing hospitalisation; require treatment with IV antimicrobials (e.g., antibiotics, antifungals, antivirals); result in persistent or significant disability/incapacity; or are, based upon appropriate medical judgement, important medical events that may not be immediately life-threatening or result in death or hospitalisation but may jeopardise the patient or may require intervention to prevent one of the other outcomes listed above [22, 27]. It may not be possible to identify all serious infections using this definition since it is not possible to assess some of its components from the secondary data sources e.g., if a particular infection prolonged an existing hospitalisation or led to disability.

Thus, for current study, the **primary outcome** serious infection will be defined as infections leading to hospitalisation, use of IV antimicrobials, or death. It will be defined as either of:

- Infections leading to hospitalisation:
 - Infection diagnosis as part of a hospitalisation episode (including primary and secondary diagnoses) (Table 16) [8, 78]
 - Infection diagnosis in primary or secondary care settings up to 7 days before hospitalisation (Table 16) [9, 79]

⁵The specific malignancies were defined based on the previously described increased or decreased risk among SLE patients when compared to the general population [12, 13, 84].

- Infections requiring treatment with IV antimicrobials:
 - Prescription/administration of IV antimicrobials (Table 19) [46, 51]
- Infection-related death:
 - Recorded diagnosis of infection (Table 16) in primary or secondary care settings with record of death within the subsequent 30 days [30].

Detailed operational definitions to identify the availability of serious infections data in different data sources as disease coding systems used will be defined in the SAP.

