The first serious infection after index date will be included. Date of each serious infection episode will be the date of infection leading to hospitalisation, use of IV antimicrobials or death, whichever occurs first. The frequency of each serious infection component – infection leading to hospitalisation, requiring treatment with IV antimicrobials and infection-related deaths – will be described as a **secondary** objective (secondary objective 8) and comparative analyses on each component will be conducted as sensitivity analysis, where possible (Section 10.7.1.7).

As **secondary outcomes**, opportunistic serious infections, other serious infections, pneumonia (overall, fatal and non-fatal) will be analysed separately (objectives 9 and $10)^6$. Additionally, the proportion of serious infections due to COVID-19 infection will be described for patients exposed and unexposed to anifrolumab.

The definition of opportunistic infections may be challenging. To define opportunistic infections detailed clinical information is often needed and, at some level almost all agents could be considered opportunistic in that they are typically more likely to occur, or present more severely in immunosuppressed patients [99]. Therefore, classifying infections as opportunistic using secondary data is challenging. In recognition of this challenge, efforts have been made by a consensus committee (which included infectious disease, public health, and pulmonary physicians with subject matter expertise in mycobacterial, fungal, viral, bacterial or parasitic infections, as well as rheumatology physicians) to harmonize a list of infections that could be considered as opportunistic for use in clinical trials and observational studies involving biologics and other disease modifying antirheumatic drugs. The consensus list of infections was based on a systematic review of several observational studies, clinical trials, case series, and expert opinion by the committee [99].

In this study, opportunistic infections are defined based on the list of infections provided by the consensus committee with two considerations: all infections that could be mapped to ICD-10 codes

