10.3.3.2 Potential confounders for the serious infection cohort

For the analysis of serious infections, potential confounders include demographics and lifestyle characteristics (as presented in Table 6), SLE history (including SLE severity, activity as detailed below) and other clinical characteristics.

Previous diagnosis of chronic infections (such as hepatitis B, hepatitis C, herpes simplex virus, among others [15] and other comorbidities may be important confounders of the association between anifrolumab and the occurrence of a serious infection. Thus, previous diagnoses of diabetes [35, 67, 81, 101], cardiovascular diseases [32], chronic renal disease [23, 30, 35, 67, 81], severe liver disease [30, 35, 48, 67], chronic respiratory diseases [30, 35, 55, 67, 101], autoimmune diseases (excluding SLE) [101], and immunodeficiencies [30] will be considered as confounders (Table 20). Before treatment, a vaccination plan against important infections is recommended for SLE patients, aiming at decreasing the risk of the serious infection [35]. Thus, vaccine administration for *Haemophilus influenzae B*, Hepatitis A and B, *Herpes zoster*, Influenza, Severe acute respiratory syndrome coronavirus 2, together with Meningococcal C and Pneumococcal vaccines (Table 23) will be included as potential confounder. Passive immunity drugs, such as immunoglobulins and monoclonal antibodies (e.g., varicella/zoster immunoglobulin, hepatitis B immunoglobulin, tixagevimab, and cilgavimab) will also be considered (Table 23).

Patients with previous infections are at an increased risk of a subsequent infection. Although patients with a serious infection in the previous 6 months will be excluded, the occurrence of nonserious infections and serious infections for more than 6 months will be considered as potential confounders. Non-serious infection will be defined as the occurrence in the previous 12 months of either a diagnosis code for infection on a primary care or outpatient setting, or community-dispensed antimicrobials (Table 19), without hospitalisation or use of IV antimicrobials.

Previous exposure to SLE SOC is associated with an increased risk of infections. Prior use of SLE drugs will be accounted for when considering the SLE severity and activity, namely the recent start of a SLE drug as captured by the activity algorithm.

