• The use of different databases (coded hospitalisations, drug prescriptions, death registries) is likely to improve sensitivity of the outcome [8], by identifying serious infections that are managed in different settings (because of the type of infection, countries' healthcare structure or access to care). Infection-related diagnoses in inpatient administrative data sources showed sensitivity ranging from 4.4–100%, depending on the type of infection (e.g., low sensitivity for sepsis), source of data, population included, and the algorithms used [8]. By considering several infection diagnoses and including diagnoses in any position (primary and secondary diagnosis) sensitivity is increased. However, specificity might decrease as infections not related with drug exposure might be more often captured. Although the definition used is likely to have high sensitivity to

capture all serious infections, data from different databases may not be available in all countries, impairing comparability.

- In France, data on IV antimicrobials may not be captured because only expensive drugs administered in the hospital setting are captured. Additionally, only data on hospitalisation diagnoses are available and it is not possible to capture data on infections coded in primary care that resulted in a hospitalisation (if that hospitalisation does not include an infection diagnosis).
- In Germany, data on inpatient IV antimicrobials administration are not captured.
- The Danish National Registries only capture data on diagnoses from secondary care (emergency, inpatient, and specialty outpatient care) and if the infection is coded as the reason for healthcare encounter.

To account for possible misclassification, narrow definitions of serious infection will be used as sensitivity analyses for the primary outcomes, by assessing and comparing the incidence of each component of the serious infection definition. However, these analyses may not be feasible if sample sizes are small for each of these serious infection components. Additionally, the management of serious infections in each country may differ, limiting generalizability.

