Appendix 3 Exemplar code lists

Code lists will be finalised in the SAP.

Table 14 Drug classes and active substances used in SLE SOC

Drug/Procedure	ATC codes
Antimalarials	
Chloroquine	P01BA01
Hydroxychloroquine	P01BA02
Quinacrine (mepacrine)	P01AX05
Glucocorticoids	
Dexamethasone	H02AB02
Methylprednisolone	H02AB04
Prednisolone	H02AB06
Prednisone	H02AB07
Triamcinolone	H02AB08
Immunosuppressive agents	
Biologic immunosuppressants	
Anifrolumab (drug of interest)	L04AA51
Belimumab	L04AA26
Rituximab (including reference product and biosimilars)	L01FA01
Synthetic immunosuppressants	
Anakinra	L04AC03
Apremilast	L04AA32
Azathioprine	L04AX01
Baricitinib	L04AA37
Cyclophosphamide	L01AA01
Cyclosporine	L04AD01
Leflunomide	L04AA13
Methotrexate	L04AX03
Mycophenolic acid/sodium ¹	L04AA06
Sirolimus	L04AA10
Tacrolimus	L04AD02
Thalidomide	L04AX02
Tofacitinib	L04AA29
Voclosporin	L04AD03
Immunoglobulins	
Immunoglobulin G	J06BA02
Plasmapheresis	
Plasmapheresis (procedure)	B05AX03

	ICD-10 codes
	C00-C96
	D00-D09
Malignancies	
-	
All haematological (malignant	C81-C96
neoplasms of lymphoid,	
haematopoietic and related tissue)	
Leukaemia	C91-95
Lymphoma	C81-88, C96
Hodgkin's lymphoma	C81
Non-Hodgkin's lymphoma	C82-86, C96
	C90
plasma cell neoplasms	
All	C00-13, C15-16, C18-23, C25, C32-34, C45, C50-
	54, C56, C60-62, C64-65, C67, C70-73
Bladder	C67
Breast	C50
Cervix uteri	C53
Endometrium	C54.1
Oesophagus	C15
Gastric	C16
Liver	C22
Lung	C33-34
Oropharynx	C09-10
Larynx	C32
Ovary	C56
Prostate	C61
Renal	C64-65
Thyroid	C73
Vagina	C52
Vulva	C51
All (melanoma and other malignant neoplasms of skin)	C43-C44
	neoplasms of lymphoid, haematopoietic and related tissue) Leukaemia Lymphoma Hodgkin's lymphoma Non-Hodgkin's lymphoma Multiple myeloma and malignant plasma cell neoplasms All Bladder Breast Cervix uteri Endometrium Oesophagus Gastric Liver Lung Oropharynx Larynx Ovary Prostate Renal Thyroid Vagina Vulva All (melanoma and other malignant

Abbreviations: ICD-10, international statistical classification of diseases tenth revision.

	ICD-10 codes
All serious infections (composite)	A00-B99, D73.3, E06.0, E32.1, G00-G02, G04.2, G05-G07, H00.0, H44.0,
[81]	H60.0, H60.1, H60.2, H60.3, H66, H67, H70, I30.1, I40.0, J00-J22, J34.0,
	J36, J38.3, J39.0, J39.1, J44.0, J85, J86, K04.4, K04.6, K04.7, K10.2,
	K11.3, K12.2, K14.0, K57.0, K57.2, K57.4, K57.8, K61, K63.0, K65.0,
	K65.9, L00-L04, L05.0, L08, N10-N12, N13.6, N15.1, N15.9, N30.0,

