	N30.8, N34.0, N39.0, N41.2, N43.1, N45, N48.2, N61, N70-N74, N75.1,
	O23, O26.4, O41.1, O75.3, O85, O86, O88.3, O91, O98, R65.0, R65.1,
	B34.2, B97.2, J12.81, J12.82, U07.1, U07.2, U10

Table 16 Exemplar code list of serious infections (composite outcome)

Abbreviations: ICD-10, international statistical classification of diseases tenth revision

Group	Subgroup	Clinical Code Description	ICD-10
	S-1	Salmonella sepsis	A02.1
	Salmonella	Localized salmonella infections	A02.2
		Respiratory tuberculosis, bacteriologically and histologically confirmed	A15
	Tuberculosis	Respiratory tuberculosis, not confirmed bacteriologically or histologically	A16
		Tuberculosis of nervous system	A17
		Tuberculosis of other organs	A18
		Miliary tuberculosis	A19
		indeterminate leprosy	A30.0
		Tuberculoid leprosy	A30.1
		Borderline tuberculoid leprosy	A30.2
	_	Borderline leprosy	A30.3
	Leprosy	Borderline lepromatous leprosy	A30.4
		Lepromatous leprosy	A30.5
		Other forms of leprosy	A30.8
		Leprosy, unspecified	A30.9
Bacterial		Pulmonary mycobacterial infection	A31.0
	Infection due to	Cutaneous mycobacterial infection	A31.1
	other mycobacteria	Other mycobacterial infections	A31.8
		Mycobacterial infection, unspecified	A31.9
	Listeriosis	Listerial meningitis and meningoencephalitis	A32.1
		Listerial sepsis	A32.7
		Other forms of listeriosis	A32.8
	Nocardiosis	Pulmonary nocardiosis	A43.0
		Cutaneous nocardiosis	A43.1
		Other forms of nocardiosis	A43.8
		Nocardiosis, unspecified	A43.9
	Systemic bartonellosis	Systemic bartonellosis	A44.0
		Legionnaires disease	A48.1
	Legionnaires disease	Nonpneumonic Legionnaires disease [Pontiac fever]	A48.2
	Vibriosis (invasive disease due to Vibrio vulnificus)	sis (invasive e due to Vibrio Vibrio vulnificus as the cause of diseases classified to other chapters	
	Progressive multifocal leukoencephalopathy	Progressive multifocal leukoencephalopathy	A81.2
Viral		Herpesviral gingivostomatitis and pharyngotonsillitis	B00.2
	Herpes simplex	Herpesviral meningitis	B00.3
		Herpesviral encephalitis	B00.4

Table 17 Exemplar code list of opportunistic serious infections

Group	Subgroup	Clinical Code Description	ICD-10
		Herpesviral ocular disease	B00.5
		Disseminated herpesviral disease	B00.7
		Zoster encephalitis	B02.0
		Zoster meningitis	B02.1
		Zoster with other nervous system involvement	B02.2
	Herpes Zoster	Zoster ocular disease	B02.3
		Disseminated zoster	B02.7
		Zoster with other complications	B02.8
		Zoster without complication	B02.9

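### The exemplar serious-infection list (Table 16) lets prevalent chronic and sequelae codes count as first events and lacks general codes for several hospitalised infections; both should be corrected before the list is final

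*Protocol*

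**What the plan says.** Section 10.3.2.2 of the protocol defines a serious infection by three routes: infection leading to hospitalisation, intravenous antimicrobials, or infection-related death. The first and third rely on Table 16.

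- **Codes.** Table 16 begins "A00-B99, D73.3, E06.0, E32.1, G00-G02, G04.2" and its last chapters include "O23, O26.4, O41.1, O75.3, O85, O86, O88.3, O91, O98, R65.0, R65.1". No part of A00-B99 is carved out.
- **Position.** The hospital component is "Infection diagnosis as part of a hospitalisation episode (including primary and secondary diagnoses" positions alike. A Table 16 code in primary or secondary care up to 7 days before an admission also qualifies.
- **Event rule.** "The first serious infection after index date will be included", and follow-up for the primary outcome then ends (Section 10.3.1.2.2).
- **History rule.** The only one for serious infection is the exclusion "A diagnosis of serious infection in the previous 6 months" (Section 10.2.2.1). Prior HIV/AIDS, congenital immunodeficiency and transplant are separate exclusions.
- **Baseline view of the same conditions.** Section 10.3.3.2 lists "Previous diagnosis of chronic infections (such as hepatitis B, hepatitis C, herpes simplex virus, among others" as possible confounders. Table 20 places H. pylori (B98.0) among gastrointestinal comorbidities. Table 22, for the malignancy cohort, lists B18.2 as a prior infection.
- **Status.** Appendix 3 states: "Code lists will be finalised in the SAP".

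**The concern.** A patient who carried chronic hepatitis before index and is later admitted for an unrelated reason, with B18 as a secondary diagnosis, meets the event definition. That record says nothing about treatment, and it ends the patient's follow-up, so a later true infection is lost to the primary analysis. In the recurrent-hospitalisation outcome (objectives 11 and 12) the same carrier can count again at each admission more than 30 days after the last qualifying discharge. For infection-related death, a chronic code followed by death from any cause within 30 days is enough.

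In the other direction, Table 16 has no general code for septic arthritis, osteomyelitis, infective endocarditis, device or post-procedural infection, appendicitis, liver abscess or cholangitis. Such admissions enter only if another qualifying code or a captured intravenous antimicrobial accompanies them.

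At stake are the incidence estimates (objectives 3 and 8) and the primary hazard ratio (objective 4). In a safety study, bias towards 1 is the unfavourable direction.

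**Working it through.** **1. Code check against the full Table 16 string.** Code meanings that the protocol does not label come from ICD-10, which Section 10.3 adopts.

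| Codes | In Table 16? |
|---|---|
| B18.1, B18.2, B90.9, B91, B92, B94.9, B98.0 | Yes, through A00-B99 |
| B37.6 (candidal endocarditis), A18.0, A39.5, A54.4, B95.6 | Yes, through A00-B99 |
| M00, M01, M46.2, M86 | No; there is no M code |
| I33, I38, I39 | No; the only I codes are I30.1 and I40.0 |
| T80.2, T81.4, T82.6, T82.7, T84.5, T84.6, T85.7 | No; there is no T code |
| K35, K75.0, K83.0 | No |

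**2. Comparison with the protocol's other tables.** Table 17 counts B18.2 as hepatitis C progression only after an earlier acute record (B17.1). Table 16 has no such condition. Table 16 cites the Swedish cohort behind the planning rate, and Section 10.5.2 says that study used infection as the primary diagnosis. The present study accepts any position, which is where carrier and sequelae codes matter most.

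**3. Can intravenous antimicrobials recover the omissions?** Section 10.9 says France captures only expensive hospital drugs, and for Germany: "In Germany, data on inpatient IV antimicrobials administration are not captured". From Table 13, France plus Germany = 74.56% + 5.40% = 79.96% of the planned sample. Table 7 lists the route as available in Denmark and Spain, 5.89% + 14.16% = 20.05%. The recurrent outcome counts only infections leading to hospitalisation, so it has no such route anywhere.

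**4. The plan's own figure.** Inputs: 1,312 exposed, 1:3 matching, 39.8 per 1000 person-years, 2 years, HR 1.5, SD(HR) 0.2, Table 13 shares. A random-effects (DerSimonian-Laird) simulation with log-HR SD = √ln(1 + (0.2/1.5)²) ≈ 0.133 and 20,000 runs gives 79.5% power, against the stated 80%. The planning figure reproduces and is not in dispute.

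**5. Over-capture, by assumption.** Let a share f of comparator events be records unrelated to exposure, occurring at the same rate in both groups, with the total comparator rate held at 39.8:

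observed HR = [1.5 × 39.8(1 − f) + 39.8f] / 39.8 = 1.5(1 − f) + f

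| f | Observed HR | Power at 1,312 (5,000 runs) |
|---|---|---|
| 5% | 1.475 | about 78% |
| 10% | 1.45 | about 75% |
| 20% | 1.40 | about 70% |
| 30% | 1.35 | about 62% |

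One way to arrive at f, again by assumption: 1-2% of patients carry such a code and have 0.2-0.4 admissions per person-year. Then 0.01 × 0.2 to 0.02 × 0.4 gives 2-8 unrelated events per 1000 person-years. The HR becomes (59.7 + 2)/(39.8 + 2) = 1.48 to (59.7 + 8)/(39.8 + 8) = 1.42, with f = 2/41.8 = 4.8% to 8/47.8 = 16.7%. This supposes the code is recorded at every admission and deducts nothing for the 6-month exclusion, for Denmark or for counting first events only. It is therefore generous.

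**6. Omission, by assumption.** If a share of true events is missed equally in both groups, with s the share still captured, HR = (1.5 × 39.8s)/(39.8s) = 1.5. Missing 5, 10 or 20% lowers the comparator rate to 37.8, 35.8 or 31.8 per 1000 person-years, with power of about 78, 76 or 75%.

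**The case against.** **Exemplar status.** Appendix 3 is a draft by its own description, Section 10.3 foresees adapting codes to each source, and Section 10.3.2.2 leaves operational detail to the SAP. This stands as far as it goes: nothing has been misanalysed. But Sections 10.3.2.2 and 10.3.2.1's neighbouring definitions of the infection outcomes point to Table 16 as the definition, and carrying it over as printed would give a poorer primary outcome.

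**Disclosed trade-off.** Section 10.9 accepts lower specificity in exchange for sensitivity and admits that some serious infections are missed. It mentions neither prevalent chronic codes nor codable infections left off the list. The planned component analyses would not reveal the problem, because hospitalisation and death use the same Table 16.

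**Partial safeguards.** These are real. The 6-month exclusion and the HIV exclusion remove some prevalent cases. Denmark identifies serious infections from primary diagnoses (Section 10.4.1.1), so the secondary-diagnosis route is closed there. Chronic infections may enter the propensity score, but balance between the groups does not stop unrelated events from diluting the hazard ratio.

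**Stronger readings a reader might infer.** One is that endocarditis, bone and joint, or device infections are absent from the outcome. They are not: B37.6 and some organism-specific codes are listed, B95-B97 and sepsis codes in secondary position qualify, and intravenous antimicrobials need no diagnosis code. Another is that B18 and every non-acute code should be struck out. That would conflict with Table 17, which counts hepatitis C progression and chronic pulmonary coccidioidomycosis (B38.1), among others. A general rule against any chronic infection already on record would also discard recurrent herpesviral events.

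**Conclusion.** The point holds as a defect to correct before the list is final. It is not an established error in the primary outcome.

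As printed, Table 16 admits prevalent chronic and sequelae codes as first events wherever secondary diagnoses count, and it lacks general codes for several hospitalised infections. Over-capture biases the hazard ratio towards 1. Omission lowers incidence and precision and, if non-differential, leaves the hazard ratio about where it was. The two errors act in opposite directions on incidence, so no net direction can be claimed.

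The size cannot be derived from the documents. The range of 1.475 to 1.40 for a true hazard ratio of 1.5 rests on an assumed 5-20% of unrelated comparator events. The 39.8 rate is itself based on primary diagnoses only, whereas the study composite is broader.

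**What to change.** Before the SAP code list is fixed:

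1. Drop the sequelae codes B90-B94.
2. Count persistent-carrier codes (B18, B98.0) only when there is no record before index. Keep the Table 17 hepatitis C progression rule and all other Table 17 codes, including recurrent herpesviral events.
3. Add M00-M01, M46.2-M46.5, M86, I33, T80.2, T81.4, T82.6-T82.7, T83.5, T84.5-T84.7, K35, K75.0 and K83.0.
4. Use the same list for the 6-month exclusion, infection-related death and the recurrent outcome.
5. Rerun the primary analysis with Table 16 as printed, as a sensitivity analysis.

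The cost is a code-list edit before extraction, one extra run, and a slight loss of comparability with the Swedish cohort behind the 39.8 rate.

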COVID-19	Pneumonia due to coronavirus disease 2019	J12.82
	COVID-19, virus identified	U07.1
	COVID-19, virus not identified	U07.2
	Multisystem inflammatory syndrome associated with COVID-19	U10
	Streptococcal sepsis	
	Other sepsis	A41
Sepsis	Systemic Inflammatory Response Syndrome of infectious origin without organ failure	R65.0
	Systemic Inflammatory Response Syndrome of infectious origin with organ failure	R65.1
	Acute tubulo-interstitial nephritis	N10
	Acute cystitis	N30.0
	Other cystitis	N30.8
	Urethral abscess	N34.0
Urinary tract infection	Urinary tract infection, site not specified	N39.0
	Gonococcal infection of lower genitourinary tract without periurethral or accessory gland abscess	A54.0
	Gonococcal infection of lower genitourinary tract with periurethral and accessory gland abscess	A54.1
	Gonococcal pelviperitonitis and other gonococcal genitourinary infections	A54.2
	Infections of genitourinary tract in pregnancy	O23
Infections During	Other infection during labour	O75.3
Pregnancy	Puerperal sepsis	085

Table 18 Exemplar code list of other relevant serious infections (including pneumonia)

Subgroup	Clinical Code Description	ICD-10
	Other puerperal infections	O 86
	Infections of breast associated with childbirth	O91
	Maternal infectious and parasitic diseases classifiable elsewhere but complicating pregnancy, childbirth and the puerperium	O98

Abbreviations: ICD-10, international statistical classification of diseases tenth revision

^a Pneumonia will be additionally analysed as a separate secondary outcome

Table 19 Exemplar code list of antimicrobials

Antimicrobials	ATC codes for Intravenous antimicrobials	ATC codes for all antimicrobials dispensed at the community pharmacy*
Anthelmintics	-	P02
Antibacterials and antiinfectives	J01	J01, D06, S01A, S01C, S02A, S03C, G01
Antimycobacterials	J04	J04
Antimycotics and antifungals	J02	J02, D01
Antiprotozoals (except antimalarials)	-	P01A, P01C
Antivirals	J05	J05, D06BB, S01AD

Abbreviations: ATC, anatomical therapeutic chemical.

* To define previous occurrence of non-serious infection.

	Diagnosis	ICD-10 codes
SLE-specific risk	Cerebrovascular disease	I60-I69
adjustment index	Chronic renal failure [30, 35, 67, 81]	N18
[97] *	Congestive heart failure	150.0
	Diabetes [35, 67, 81, 101]	E10-E14
	Moderate or severe liver disease [30, 35, 67, 81]	K70-K77
	Myocardial infarction	I21, I22
	Nephritis	N00, N01, N03, N05
	Pericarditis [51]	I30, I32
	Peripheral vascular disease	173

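### The prior non-serious infection covariate is coarser than the planned dispensing data allow, and its antiprotozoal codes contradict their own label

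*Protocol*

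**What the plan says.** Section 10.3.3.2 gives the reason for the covariate: "Patients with previous infections are at an increased risk of a subsequent infection". It defines prior non-serious infection as the occurrence, in the previous 12 months, of either an infection code in primary or outpatient care, "or community-dispensed antimicrobials (Table 19), without hospitalisation or use of IV antimicrobials". The two arms are alternatives. The dispensing arm has no condition on route, number of courses, duration of supply or a linked diagnosis.

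The community-pharmacy column of Table 19 (Appendix 3) is footnoted "To define previous occurrence of non-serious infection". Its antibacterial row is "J01, D06, S01A, S01C, S02A, S03C, G01". The antifungal row adds D01 to J02, and J04 and J05 are also included. The row labelled "Antiprotozoals (except antimalarials" lists P01A and P01C as whole groups. Table 14 places "Quinacrine (mepacrine" under antimalarials with code P01AX05.

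On data, Section 10.9 says of France that "only data on hospitalisation diagnoses are available". Section 10.4.1.1 says Denmark has no data on conditions managed only by a general practitioner or a private-practice specialist. Appendix 3 calls its code lists exemplar and leaves their final form to the SAP.

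**The concern.** Previous infection is listed in Table 6 as a propensity-score candidate for the serious infection cohort only. This covariate is the part of it meant to capture community infections that never reached hospital. If it cannot separate a patient with one tube of antibacterial cream from a patient with four systemic antibiotic courses, balancing it leaves part of the difference in infection-proneness in place. That difference then enters the primary serious infection hazard ratio (objective 4).

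The antiprotozoal row raises a narrower problem. A drug the protocol treats as lupus therapy can be scored as an infection, against the row's own label.

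**Working it through.** **1. Codes against labels.** Mepacrine is P01AX05 (Table 14), so it lies inside P01A (Table 19). The label excludes antimalarials and the code includes one. Chloroquine (P01BA01) and hydroxychloroquine (P01BA02) lie in P01B, which is not listed, so the conflict concerns mepacrine alone. Table 7, footnote e, says mepacrine is not marketed in France or Germany. The overlap can therefore arise only in Denmark and Spain: (89 + 216)/1,435 = 21% of expected infection-cohort initiators (Table 8), and only among mepacrine users there.

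**2. Where the dispensing arm dominates.** France supplies 1,005/1,435 = 70% of expected initiators and has no routine community infection diagnoses, so the covariate there rests on dispensing. Denmark adds 89, giving (1,005 + 89)/1,435 = 76%. Denmark does record emergency and specialty outpatient diagnoses (Table 7, footnote d), so its dependence is only partial.

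**3. What a coarse flag can do.** The protocol states no figure to reproduce. The following is an illustration with assumed inputs. Let a share p1 = 0.35 of exposed patients and p0 = 0.25 of comparators be truly infection-prone, with risk ratio RR = 2 or 3 for serious infection.

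- Unadjusted bias = [1 + p1(RR − 1)] / [1 + p0(RR − 1)]. For RR 2 this is 1.35/1.25 = 1.080; for RR 3, 1.70/1.50 = 1.133.
- Flag prevalence: c1 = p1·se + (1 − p1)(1 − sp), and c0 likewise with p0.
- With the flag perfectly balanced, the share of prone comparators becomes e0 = c1·p0·se/c0 + (1 − c1)·p0(1 − se)/(1 − c0).
- Residual bias = [1 + p1(RR − 1)] / [1 + e0(RR − 1)].

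Worked case, se 0.98 and sp 0.70: c1 = 0.343 + 0.195 = 0.538; c0 = 0.245 + 0.225 = 0.470; e0 = 0.538 × 0.245/0.470 + 0.462 × 0.005/0.530 = 0.285. For RR 2 the residual is 1.35/1.285 = 1.051, and ln 1.051/ln 1.080 leaves 64% of the bias.

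| Sensitivity / specificity | Residual, RR 2 | Residual, RR 3 | Log bias left |
|---|---|---|---|
| 0.98 / 0.30 | 1.073 | 1.121 | 91% |
| 0.98 / 0.45 | 1.067 | 1.110 | 84% |
| 0.98 / 0.70 | 1.051 | 1.083 | 64% |
| 0.90 / 0.80 | 1.047 | 1.077 | 59–60% |
| 0.80 / 0.85 | 1.049 | 1.080 | 62% |

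Moving from the worst flag to one of the better measures changes the hazard ratio by between 1.073/1.049 = 1.023 and 1.121/1.077 = 1.041, that is 2 to 4%. If the flag's specificity is already 0.70, the gain is under 1% (1.051/1.047 = 1.004; 1.083/1.077 = 1.006).

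**4. Narrowing alone is not the answer.** With p1 = 0.40 and p0 = 0.25 or 0.30, a flag with sensitivity 0.9 removes 59–61% of the bias at specificity 0.9, 28–32% at 0.7, 13–15% at 0.5 and 4–5% at 0.3. A narrow flag with sensitivity 0.6 and specificity 0.95 removes only 39%. Losing sensitivity also costs control.

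**The case against.** The best defence is that Table 19 is an exemplar and the SAP will finalise it. Section 10.3.3.2 speaks of an occurrence and does not fix how the variable enters the propensity score. Treated skin, eye, ear and vaginal infections are non-serious infections, so counting them fits the definition. Where outpatient diagnoses are missing, as in France, a sensitive list is a reasonable choice. Most of this stands. It argues against deleting topical products, but not against separating them from systemic courses. Deferral of the lists does not change the either/or rule in Section 10.3.3.2, and it does not excuse a row whose code contradicts its label.

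A reader might infer three stronger things that the protocol does not support:

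- That infection-proneness is barely adjusted for. This needs a specificity of about 0.5 or less, which the protocol neither gives nor implies. It also overlooks the exclusion of patients with a serious infection in the previous 6 months. The other candidates would have to be ignored too: earlier serious infections, chronic infections, comorbidities, immunodeficiencies, vaccines, passive-immunity drugs, SLE severity and activity components, and standard of care. These are not complete everywhere (Table 26 shows vaccination unavailable in Denmark and Germany), but they are not nothing.
- That comparators on prophylaxis are being matched to patients with recurrent infection. The protocol never mentions anti-infective prophylaxis. Long-term supply is simply not distinguished from treatment.
- That lupus antimalarials in general count as infections. Only mepacrine does.

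**Conclusion.** The point holds in limited form. The label and code of the antiprotozoal row conflict, and this should be corrected, though its reach is small. The covariate treats a single topical dispensing as equal to repeated systemic courses, and this matters most in France, where dispensing is the main community signal. It is a weak measure of infection-proneness.

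The resulting bias in the serious infection hazard ratio is not quantified by anything in the protocol, and its direction is unknown. Under the assumed inputs above, the avoidable part is at most about 2 to 4%, against a planning hazard ratio of 1.5, and near zero if specificity is around 0.70. That range treats this covariate as the only control for infection-proneness; the 6-month exclusion and the other propensity-score candidates should offset part of it. The case for acting is that the better measure uses data already planned and can be set before extraction.

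**What to change.** In Table 19, exclude P01AX05 from P01A so that the codes match the label. In Section 10.3.3.2 and the SAP:

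- Enter the number of systemic anti-infective courses (J01, J02, J04, J05) in the previous 12 months as a graded propensity-score covariate: 0, 1, 2, 3 or more.
- Keep topical and local products (D01, D06, G01, S01A, S01C, S02A, S03C) as a separate indicator. D06BB and S01AD, listed under antivirals, already fall within D06 and S01A.
- Count continuous uninterrupted supply as one episode, with its own indicator. This should be defined by supply pattern, because outpatient indication is not recorded in France (Section 10.4.1.2) and indication is not recorded in Germany (Section 10.4.1.3).
- State which term takes P02, P01C and the rest of P01A.

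The cost is a table edit, slightly more programming on the same dispensing records, and a few more propensity-score terms. Those extra terms will be felt most in the small sources: Denmark expects 89 infection-cohort initiators and Germany 126.
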